### *Control group*

Participants randomised to the control group can continue with usual medical care while on the waiting list to receive their multidisciplinary pain management program at the RPAH Pain Management Clinic. At the conclusion of this study, participants in this group will be provided with an art making kit and tickets to the AGNSW, as compensation for their time and participation in the project.

### *Endpoints/Outcome Measurements*

#### *Quantitative Approach*

To assess patient demographics and pain-related medical history, we will seek participants' permission to access the results of their ePPOC questionnaires (electronic Persistent Pain Outcomes Collaboration, Appendix 2). These questionnaires are required as part of admission to the pain management programs in Australia. After gaining informed consent, previously completed ePPOC questionnaires will be accessed and recorded. We briefly provide information on the items extracted from ePPOC data. For detailed information, please refer to Appendix 2. We will extract the following items from ePPOC questionnaires:

1. Patient demographic information:

In ePPOC analysis and reporting, patient information defines the patient population and contextualises the patient outcomes. We will record: sex, age, height (cm), weight (kg), postcode, and country of birth.

2. Pain History:

- *Episode information:* An episode is defined as a continuous period of care for a patient in one pain management service. Under this definition, a patient may have more than one episode. For example, a patient may receive treatment for pain at more than one pain management service or be re-referred to a service following completion of a previous episode. There should however, be only one active episode at any one time for a patient at a pain management service.

The information collected at the episode level reflects the circumstances at the beginning of the episode. We will record Patients' referral date for the current pain episode, episode start date, episode start mode (how the episode began), cause of pain, pain duration (the length of time for which the patients' pain has been present, comorbidities (comorbid conditions the patient has at the start of the episode of care).

---

 ePPOC is a program which aims to help improve services and outcomes for individuals experiencing chronic pain through benchmarking of care and treatment.

- *Pathway information:* The “Pathway” describes the type of treatment the patient receives/has received during the episode of care. Pathways generally begin after education/orientation programs and appointments designed to assess the patient and determine the most appropriate treatment pathway. There are four primary pathways:
  - Pathway 1 Group pain management program(s) (PMP)
  - Pathway 2 Individual appointments with clinicians (e.g. medical, nursing and allied health practitioners)
  - Pathway 3 Concurrent pathways where group programs and individual appointments are provided at the same time
  - Pathway 4 One-off interventions, where it is not expected that any further intervention will be provided. These might include a procedural intervention with no further individual appointments planned, or a single appointment with a medical specialist.
  
- *Service information:* Service information describes the service events (also known as occasions of service) a patient receives during an episode of care. These include individual appointments with a physiotherapist (or nurse, psychologist, specialist), multidisciplinary assessments and discussions, pain management programs, procedures, education/orientation programs. This information is collected to understand what treatments the patient is receiving while enrolled in our study.
  
- *Health service utilisation* in the last three months (medical, allied health, emergency services and diagnostic tests)
  
- Work status and productivity measured on a 0-10 rating scale

### 3. Patient reported outcome measures:

As part of ePPOC, standardised patient questionnaires are completed by the patient in ‘referral’ and ‘follow-up’ questionnaires at:

- initial referral to the pain management service;
- the beginning and end of each pathway within an episode; and
- follow-up three to six months after the end of the episode.

While we will use the recorded data from ePPOC, we will also assess and record following outcome measures at commencement and at the end of our art intervention in both groups. Patient reported outcome measures are:

- *Pain description:* Patient is asked to choose or describe the following items:
  - Frequency of their pain (e.g., always present, occasionally present, etc).

- Pain site: report of where on a body map the patient feels pain.
  - Pain severity: The patient is asked to rate the intensity of their pain at its worst in the last week, at its least in the last week, on average, and right now. For each of the four questions above, the patient rates their pain on a scale of 0 to 10, where 0 = 'No pain' and 10 = 'Pain as bad as you can imagine'.
  - Rating of their change-overall (on a scale of -3 to 3 where -3 is 'very much worse', 0 is 'unchanged' and '3' is 'very much better'.)
  - Rating of their change-physical abilities (on a scale of -3 to 3 where -3 is 'very much worse', 0 is 'unchanged' and '3' is 'very much better'.)
  - Pain interference: The patient is asked to rate how much their pain has interfered with the following in the past week: general activity, mood, walking ability, normal work (both outside the home and housework), relations with other people, sleep, enjoyment of life. For each of the seven questions above, the patient rates their pain on a scale of 0 to 10, where 0 = 'Does not interfere' and 10 = 'Completely interferes'. An average rating of pain interference is calculated by summing the scores for the seven questions above, divided by the number of questions the patient completed. If more than one number has been circled for a question, use the highest score.
- *Depression, Anxiety, Stress Scale 21 (DASS21)*: The DASS is a set of three self-report scales designed to measure the negative emotional states of depression, anxiety and stress. ePPOC uses the short version of the DASS, the DASS21. The patient is asked to read the 21 statements and indicate how much the statement applied to them over the past week. For each of the statements, the patient indicates how much the statement applied to them according to the following scale:
- 0 – did not apply to me at all;
  - 1 – applied to me to some degree, or some of the time;
  - 2 – applied to me to a considerable degree, or a good part of the time; and
  - 3 – applied to me very much, or most of the time.
- For details on how to measure and interpret the final score, please refer to Appendix 2, Pages 26-27
- *Pain Self-Efficacy Questionnaire (PSEQ)*: The PSEQ is a measure of how confident a patient is that he or she can do a range of activities despite their pain. The patient is asked to read the 10 statements and rate how confident they are that they can do the tasks at present.

For each of the statements, the patient indicates on a scale of 0 to 6 how confident they are, where 0 = "Not at all confident" and 6 = "Completely confident". The sum of scores for all items provides a total score. Higher scores indicate higher levels of self-efficacy.

For details on how to measure and interpret the final score, please refer to Appendix 2, Page 28.

- *Pain catastrophising scale (PCS)*: The PCS is a measure of an individual's thoughts and feelings relating to their pain. The scale includes three sub scales measuring the dimensions of Rumination, Magnification and Helplessness.

The patient is asked to read 13 statements describing different thoughts and feelings that may be associated with pain and indicate the degree to which they have these thoughts and feelings when they are experiencing pain. For each of the statements, the patient indicates the degree to which they have these thoughts and feelings, according to the following scale:

- 0 - Not at all
- 1 - To a slight degree
- 2 - To a moderate degree
- 3 - To a great degree
- 4 - All the time

Total and subscales are calculated by summing the scores for the relevant items. For details on how to measure and interpret the total and subscale scores, please refer to Appendix 2, Pages 29-30.

- *Medications related information*: Records whether the patient is taking medications, based on the response provided in the Medication Use section of the ePPOC questionnaires.

#### 4. Saliva Cortisol Level:

Cortisol is the stress hormone biomarker used routinely in the monitoring of psychological and certain aspects of physiological well-being. The ability to monitor stress in a quick and easy non-invasive manner is possible by administering a saliva test. Saliva Cortisol level will be assessed using the IPRO Cortisol LFD. The IPRO Cortisol LFD is a non-invasive, quick and quantitative method of assessment that requires no laboratory equipment. The component parts required for a test are: an IPRO LFD Reader; an IPRO Oral Fluid Collector (OFC) swab; an IPRO OFC Buffer and an IPRO LFD cassette. The Cortisol can be gained within 12-13 minutes from giving the subject an IPRO OFC swab. One of the advantages of salivary Cortisol is that it represents the unbound "free" and thus biologically active component of this stress hormone.

In the intervention group, participants' saliva samples will be collected before, during and after each art intervention session, at specific time points (3 samples over each session, for each participant). Our trained research assistant will read and record the saliva Cortisol levels after collection of saliva.

In the control group, saliva Cortisol level will be once at baseline and once within five weeks. We intend to collect Saliva samples from the control group at a specific time point that matches the time point of intervention group during the day, after art intervention. The specific time points will be finalised once the art sessions are confirmed with the Art Gallery.

#### 5. Heart Rate

Participants' heart rate will be monitored and recorded at the same time as the collection of saliva samples. To record the heart rate, the Instant Heart Rate mobile application will be used. The application uses mobile phone's camera flash to measure heart rate in seconds. Participants place the tip of their index finger over the camera and wait for Instant Heart Rate to detect colour changes in the fingertip each time the heart beats.

#### 6. A self-reported journal:

Participants in both groups will be provided with a journal to document any changes or improvements regarding their mood, activities, medications, healthcare visits, pain behaviour or intensity over five weeks. This Journal is provided in Appendix 3 (My Pain Diary).

#### *Qualitative Approach*

In this pilot study we will undertake exploratory, open ended qualitative research that seeks to understand the social, psychological and experiential dimensions of visual arts creation in individuals with chronic pain. As this is a pilot, exploratory study, our approach will not be guided by commitments to any particular methodology. Rather we will take a broadly constructivist and interpretive approach to the collection and analysis of data. We characterise our approach as constructivist because the team is interested in how participants construct and reconstruct their sense of identity through the process of visual art creation, and how they present and understand their experiences. We also characterise our approach as interpretive because the researchers will be constantly interpreting the data as we encounter it, triangulating analysis from our different disciplinary backgrounds and perspectives.

#### Process:

1. The final hour of each session will be allocated to a group discussion and reflection on the art creation process, effectively a group interview, conducted jointly by team members [name], a rehabilitation counsellor, and [name], a qualitative health researcher. This group interview is similar to a 'focus group' and is understood partly as

'action research' in which reflections prompted by the discussion may influence their experiences in the subsequent session.

2. It is expected that after two hours of art making, the participants will stand back from their works and have a 1 hour 'focus group' / reflective session. However, we think it is important to collect data during the entire 3-hour session, as it is possible that there will not be such a clear disjunction between the art making and the reflection, with the former going for longer and the latter occurring throughout. Because the art creation process values unpredicted emergences, the research design is somewhat flexible, and the team has created processes of iterative discussion and triangulation in order to preserve rigour and simultaneously be responsive to participants' developing experiences.
3. The entire 3-hour session will be recorded. The facilitator will wear a lapel microphone for this purpose and a Phillips digital audio recorder with four boundary microphones which will be used to record conversations between the facilitators and participants.

Group Interviews: Question route:

The question route for the group interviews will be open-ended as this is appropriate for an exploratory pilot study. However, we will use a loose structure to the group interviews. Each interview is anticipated to begin with a free association in which participants step back from the artwork they have created and write down as many terms as they can think of that relate to their art work

The question route will explore:

- How did you experience today's session?
  - How did you feel at the beginning?
  - Did your feelings or experience change over the session?
  - What are 3 words that describe your experience in this session?
- What were you thinking about when you began your painting?
- How does your pain, and your painting, look when you step back from it?
- Did the painting change as it developed?
- Did your understanding of yourself or of your pain change as you painted?
- Is painting or creative art making something you'd like to continue more in the future?

*Confounders*

- Socialisation, discussion of the art works and exposure to other art works at the gallery have the potential to improve the outcome measures. These experiences are all included in the art creation process and cannot be separated.

- Other treatments undertaken as part of routine medical care. We will collect information weekly to monitor if our participants have changed their medications or seen another healthcare provider.

#### *Statistical Considerations/Data analysis (Quantitative)*

Statistical support will be sought from the Faculty of Health Sciences Biostatistician ([name]). Descriptive statistics will be used to describe the population, patient-reported outcome measures and physiological outcome measures. Data will be assessed for normality. Generalized linear models will be used to compare the mean change in outcomes (continuous variables) from baseline to each time point between the intervention and control groups. This will provide effect estimates and 95% confidence intervals for any difference between the intervention and control group.

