### *Randomisation*

The Participant Information Statement and Consent form will be emailed to participants who meet the inclusion criteria. The project research assistant will then contact participants by phone to provide detailed information about the project, research process, and participation requirements and answer any questions they may have.

People who agree to participate by signing the consent form will be randomised to either the intervention group or control group. Our randomisation approach will be impacted by the number of participants recruited from the STEPs Program.

- If we are successful in recruiting 20 patients after attending one of the monthly STEPs programs, participants will be randomly allocated by the research team to either intervention or control group, using a computer-generated sequence and a 1:1 allocation ratio.
- If we are not successful in recruiting 20 patients from one STEPs program, we aim to use the quasi-randomisation approach. That is, the first group of participants recruited from the first STEPs program will be allocated to the intervention group and participants recruited from the next STEPs program will be allocated to the control group.

This approach will not extend the waiting time of patients to receive their pain assessment and treatment, should we not succeed in recruiting 20 participants via the first STEPs program.

Participants will be notified by phone/email of their group and intervention participants will be notified about their first session of art observation and creation at the Art Gallery of NSW.

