### *Study Procedure*

After receiving consent, participants will be randomised into an intervention or a control group. The intervention group will undergo a five sessions of art intervention. The assessments will take place in both groups at baseline, at post intervention (at conclusion of 5 sessions), 3 months, 6 months and 12 months' time points. In addition, several measurements will be

collected throughout the intervention sessions including saliva samples, pain behaviour using a pain diary, and heart rate using a mobile app. For the control group, the treatment will be as usual (they will be on the waitlist to receive their pain treatment), and they will be offered two tickets to visit the art gallery and art creation tool kit, once the study is concluded.

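### The quantitative analysis fixes change from baseline as the compared quantity and names no baseline covariate; adding one is nearly free and would usually sharpen the estimates

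*Protocol*

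**What the plan says.** Under Statistical Considerations/Data analysis (Quantitative), the protocol states: "Generalized linear models will be used to compare the mean change in outcomes (continuous variables) from baseline to each time point", with intervention and control as the groups compared. It adds: "This will provide effect estimates and 95% confidence intervals for any difference between the intervention and control group". The section names no covariate. It neither includes the baseline value nor rules it out.

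Baseline values will exist. Study Procedure says: "The assessments will take place in both groups at baseline, at post intervention (at conclusion of 5 sessions), 3 months, 6 months and 12 months'".

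The Randomisation section gives two routes. The first is conditional: "If we are successful in recruiting 20 patients after attending one of the monthly STEPs programs", participants are allocated at random "using a computer-generated sequence and a 1:1 allocation ratio". Otherwise allocation follows the programme attended: "the first group of participants recruited from the first STEPs program will be allocated to the intervention group", and those from the next programme form the control group.

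The Outcomes section says that the pilot's results will be used to choose outcome measures and sample sizes for later studies.

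**The concern.** Subtracting baseline is the same as fitting baseline with its slope fixed at 1. When baseline and follow-up have similar variances, the true slope is roughly their correlation, which is below 1. Two things follow.

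- **Precision.** At low to moderate correlation, subtraction adds baseline noise to the response, and the interval is wider than the data require.
- **Imbalance.** If one arm happens to start higher, subtraction removes more than the expected carry-over. That arm then appears to fall further than it should.

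Averaged over all possible randomisations the change score is unbiased. The distortion is conditional on the imbalance that actually occurs, and with about 10 per arm a sizeable one is not rare. Several outcomes are measured (pain severity and interference, DASS21, PSEQ, PCS), and their estimates are meant to guide the choice of outcomes and the sample size of a later trial.

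**Working it through.** The protocol gives no power, SD, effect size or calculated sample size, so there is no figure of its own to reproduce. The check compares the expected 95% interval with and without a baseline term.

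**Inputs**
- N = 20 and n = 10 per arm: the Randomisation section's threshold of 20 with 1:1 allocation. It is a recruitment threshold, not a calculated sample size.
- Confidence level 95%: quantitative analysis section.
- Baseline/follow-up correlation ρ: not in the documents. It is assumed and shown over a range.
- Also assumed: equal SDs at baseline and follow-up, roughly normal data, and complete follow-up.

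**Formulas for the half-width, in units of the outcome SD**
- Change score: t(18) × √[2(1−ρ) × 2/n], with t(18) = 2.101.
- Baseline-adjusted: t(17) × √[(1−ρ²) × (2/n) × (1 + 1/(N−4))], with t(17) = 2.110. The factor 1 + 1/16 = 1.0625 is the cost of estimating the slope.

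**Example, ρ = 0.5**
- Change score: 2.101 × √(1.0 × 0.2) = 2.101 × 0.447 = 0.940.
- Adjusted: 2.110 × √(0.75 × 0.2 × 1.0625) = 2.110 × 0.399 = 0.842.
- Ratio: 0.842/0.940 = 0.896, or 10.4% narrower.

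| ρ (assumed) | Change score | Adjusted | Difference in width | Single simulated trials with the adjusted interval narrower |
|---|---|---|---|---|
| 0.3 | 1.112 | 0.928 | 16.5% narrower | 91% |
| 0.5 | 0.940 | 0.842 | 10.4% narrower | 80% |
| 0.7 | 0.728 | 0.695 | 4.6% narrower | 63% |
| 0.8 | 0.594 | 0.584 | 1.8% narrower | 50% |
| 0.9 | 0.420 | 0.424 | 0.9% wider | 37% |

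The last column comes from 8,000 simulated trials per correlation. Their mean widths gave ratios of 0.832, 0.894, 0.951, 0.980 and 1.007, in line with the formulas.

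**Break-even.** Setting the two half-widths equal gives 1 + ρ = 2 × t(18)² / (1.0625 × t(17)²) = 1.867, so ρ is about 0.87.

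**Imbalance.** The baseline difference between arms has SD √(2/10) = 0.447. The probability that it exceeds 0.5 SD in either direction is P(|Z| > 0.5/0.447 = 1.118) = 0.26. Given a baseline difference of 0.5 SD, the expected shift in the change-score comparison is −(1−ρ) × 0.5:
- ρ = 0.5: −0.25 SD
- ρ = 0.7: −0.15 SD

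**Fit with the planned model.** In the simulations, adding baseline to a model for change gave the same interval for the arm difference as modelling the follow-up value with baseline as covariate (differences below 1e-15). The planned response can therefore stay as it is.

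**The case against.** The strongest reply is that silence is not exclusion. A generalized linear model for change can carry baseline, the section says that a biostatistician will be consulted, and covariates are often settled in a statistical analysis plan, which is not shown here. That stands as far as it goes: the documents do not show that baseline adjustment has been rejected. But the protocol does fix the compared quantity as mean change, and a reader following it literally would run an unadjusted change-score comparison. The point is to close that gap.

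Several stronger readings are tempting and are not supported.

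- **That every interval is widened.** There is no expected gain above a correlation of about 0.87, and single trials vary. The inclusion criteria ask for pain that has been stable for three months, so fairly high correlations for pain are plausible. The ratings of overall change and of change in physical abilities, on a −3 to 3 scale, have no baseline to adjust for.
- **That imbalance is left uncorrected.** The direction is the opposite: subtraction over-corrects it.
- **That each time point is fitted separately, ignoring within-person correlation.** Comparing change to each time point names the contrasts, not the model structure.
- **That intervals will use normal quantiles and be too narrow.** No reference distribution or software is named.
- **That 20 is the trial's sample size.** It is the threshold for the randomised route.

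The fallback also limits the remedy. If the first cohort is all intervention and the next all control, baseline differences need not be chance. Adjusting for baseline then does not remove confounding, and its advantage over change scores is not assured.

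**Conclusion.** The point holds as a free improvement of minor to moderate importance. For continuous outcomes with a baseline value, under the randomised route with 10 per arm, a baseline term gives a modest expected gain in precision at correlations of 0.3 to 0.8 and a negligible loss at 0.9. It also removes the regression-to-the-mean shift caused by chance imbalance, which is the more useful benefit in a pilot whose estimates will inform later planning.

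The size rests on the assumed correlations, equal variances and complete data. With fewer participants followed, the cost of estimating the slope rises somewhat. Nothing here shows that the planned analysis is invalid under randomisation.

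**What to change.** Add to Statistical Considerations/Data analysis (Quantitative):

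> For each continuous outcome with a baseline measurement, the model will include the participant's baseline value of that outcome as a covariate. Differences between arms will be reported with t-based 95% confidence intervals. Ratings that are themselves judgements of change will be compared without a baseline term. If allocation is by STEPs cohort, estimates will be reported as non-randomised comparisons.

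Two cautions on wording:
- Do not add a STEPs cohort term. A second cohort arises only in the fallback, where cohort and arm coincide and their effects cannot be separated.
- Do not prescribe an arm-by-time model for every outcome. For cortisol the protocol says "In the control group, saliva Cortisol level will be once at baseline and once within five weeks", so the controls have a single post-baseline value and only one adjusted contrast is possible.

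The cost is a few lines of text and one degree of freedom per comparison (18 to 17 at N = 20). No new data are needed.
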